•	Section 8.1.6 (Photography, Newly Added)	Removed text from Sections 8.1.2 and 8.1.3: "Photographic images of the lesion will be taken as part of source documentation, wherever possible."	
•	Section 1.3 (SoA); Section 10.10.2 (Substudy SoA)	Added contraception check at each visit	Updates in SoA and substudy SoA
•	Section 8.2.5 Clinical Safety Laboratory Assessments Section 10.2 (Appendix 2: Clinical Laboratory Tests); Section 10.10.2 (Substudy SoA); Section 10.10.7.2 (Substudy Early Termination/End of Treatment Visit)	Added laboratory tests at EoT visit of the substudy. Updated substudy SoA and relevant sections.	Updates in substudy SoA and relevant sections
•	Section 10.10.2 (Substudy SoA)	Added text in time frame for substudy follow-up visit	Updates in substudy SoA for clarity
•	Section 1.3 (SoA)	Added Weight measurement at Baseline	Updates in SoA
•	Section 10.10.2 (Substudy SoA)	Added vital signs measurement at all visits	Updates in substudy SoA
•	Section 1.1 (Synopsis) Section 9.4 (Interim Analysis) Section 10.10.10.4 (Substudy Interim Analysis)	Added text: As this is an open-label study, the sponsor may conduct reviews of the data, including MRI data, (newly added) during the course of the study for the purpose of safety assessment or to support regulatory	To clarify on interim analysis, and further define the range and purpose of data review

submissions (newly added).	
There will be no formal (newly added) interim	
analysis for this substudy. The sponsor may conduct reviews of the data, including MRI data, during the course of the study for the purpose of safety assessment or to support regulatory submissions (newly added).	
Added text: "Descriptive statistics for change from baseline in POEM and ADCT scores will be derived at all scheduled timepoints, for each treatment arm."	To clarify on secondary PRO endpoint analysis
 Revised "Abnormal developmental bone findings related to study intervention", "abnormal bone findings", "abnormal findings" in knee MRI- related sections to "Bone safety findings" 	To correct an editorial error and keep consistency with the program objective

1. PROTOCOL SUMMARY

1.1. Synopsis

Protocol Title: A randomized, open-label, parallel-group study to evaluate the safety and efficacy of abrocitinib 100 mg and 200 mg tablets in participants aged 12 years and older with moderate to severe atopic dermatitis in India

Brief Title: A Safety and Efficacy Study of Abrocitinib Tablets in Participants Aged 12 Years and Older with Atopic Dermatitis in India

Rationale:

The causes of AD are varied. Both a genetic predisposition and numerous trigger factors play an important role in the first manifestation and in exacerbations of the disease.

As per the Indian consensus statement for management of AD, patients with AD suffer from dry skin and defective skin barrier function, that manifests mainly as pruritus. Systemic therapy is used to treat patients with moderate to severe AD on failure of topical treatments. Currently approved systemic agents in India have modest efficacy in patients with moderate to severe AD but are associated with adverse events that often limit long-term use.

Abrocitinib is an oral, once daily JAK1 selective inhibitor under investigation for the treatment of moderate to severe AD. Selective inhibition of JAK1 with abrocitinib modulates signaling by IL-4, IL-13, and other cytokines (eg, IL-31, IL-22, and TSLP) involved in the pathogenesis of AD and pruritus while sparing JAK2 inhibition and minimizing the risk for neutropenia and anemia. Inhibition of neuronal JAK1 dependent pathways has also been shown to ameliorate pruritus.¹

This study is planned to provide additional safety and efficacy data for abrocitinib in India.

Objectives, Endpoints, and Estimands

Objectives	Endpoints	Estimands
Primary:	Primary:	Primary:
• To evaluate the safety of abrocitinib in participants aged 12 years and older with moderate to severe AD.	Incidence of AEs and SAEs.	• The primary estimand for safety is the incidence of AEs and SAEs in participants aged 12 years and older with moderate to severe AD, from the time of first dose to Week 16, regardless of dosing compliance or treatment discontinuation.
Secondary:	Secondary:	Secondary:
• To assess the efficacy of abrocitinib in participants aged 12 years and older with moderate to severe AD.	 Response based on IGA score of clear (0) or almost clear (1) and greater than or equal to 2 points improvement from baseline at Week 12. Response based on achieving ≥75% improvement from baseline in the EASI total score (EASI-75) at Week 12. Response based on ≥75% improvement in SCORAD (SCORAD75) at Week 12. Change from baseline in POEM at Week 12 and at all scheduled time points. Change from baseline in ADCT at Week 12 and at all scheduled time points. 	• The secondary estimand is the treatment effect of abrocitinib on participants aged 12 years and older with moderate to severe AD, based on IGA response, EASI-75 response and SCORAD75 response from baseline to Week 12, considering patients who discontinued treatment as non-responders and based on outcome measures of POEM and ADCT from baseline to Week 12 and at all scheduled time points. Data collected after treatment discontinuation is excluded.
Primary substudy objective(s):	Primary substudy endpoint (as secondary endpoints for B7451094):	Primary substudy estimand(s):
• To evaluate the potential effects of abrocitinib on bone development in adolescent participants 12 to <18 years of age, as assessed by knee MRI.	• The proportion of bone safety findings in knee MRI 1 year after randomization in adolescent participants exposed to abrocitinib 100 mg and 200 mg QD.	• The primary substudy estimand is the incidence of bone safety findings in knee MRI after 1 year of being exposed to abrocitinib in adolescent participants 12 to <18 years of age, regardless of dosing compliance or treatment discontinuation.

Overall Design

Brief Summary

This is a randomized, open-label, parallel-group study to assess the safety and efficacy of orally administered tablets of abrocitinib 100 mg and 200 mg QD in participants aged 12 years and older with moderate to severe AD in India. There is a planned treatment duration of 12 weeks, with 4 weeks of off-treatment safety follow up thereafter. Study participants will be screened within 28 days prior to the first dose of study intervention to confirm that they meet the eligibility criteria for the study.

This study protocol also includes a substudy evaluating whether abrocitinib has any potential effects on adolescent bone with regard to bone safety findings in knee MRI. Adolescent participants (12 to <18 years of age) will continue to receive study intervention until 1 year after randomization into the main study. Section 10.10 (Appendix 10) contains complete information regarding the substudy.

Number of Participants

Approximately 200 participants will be enrolled and randomized to study intervention at approximately 10 sites in India. Adolescent participants 12 to <18 years of age will be enrolled in the knee MRI substudy.

Intervention Groups and Duration

Participants who meet eligibility criteria at baseline will be randomized in a 1:1 ratio to receive abrocitinib 200 mg in tablet form (100 mg tablet \times 2) (n=100) or abrocitinib 100 mg (100 mg tablet \times 1) (n=100) taken once daily by mouth. The total treatment duration will be 12 weeks with a 4-week off-treatment safety follow-up period for the main study, and 1 year treatment period for adolescent participants enrolled in the knee MRI substudy.

Data Monitoring Committee or Other Independent Oversight Committee: Yes

Safety Adjudication Committees:

To independently assess the specific, complex safety events related to malignancies, cardiovascular events, and opportunistic infections (including eczema herpeticum and other infections of special interest) in this study, Safety Adjudication Committees, consisting of clinical experts in each of the relevant clinical areas, will be set up to harmonize and standardize assessments. In order to allow for an unbiased safety assessment, the members of these committees will be blinded to treatment assignment. Further information about the Safety Adjudication Committees will be defined in their respective charters, including a specific description of the scope of their responsibilities, a plan where communication timelines are defined, and the exact process and definitions used by each committee to adjudicate the safety events that they will adjudicate. Other safety events for adjudication may be identified and included in the remit of the Safety Adjudication Committees as appropriate. A separate safety adjudication committee will be established for the MRI substudy for bone findings.

[figure not shown]
Statistical Methods

A sample of 200 participants (100 randomized participants per treatment arm) would allow estimation of the incidence rate of any AE with maximum margin of error of 10%, in each treatment arm. All randomized participants who receive at least 1 dose of abrocitinib will be included in the analyses. The number and percentage of treatment-emergent AEs will be summarized according to type, frequency, severity, seriousness and relationship to abrocitinib in each treatment arm. The response rates, together with the corresponding

95% CI (using the normal approximation or Clopper-Pearson exact method, whichever is appropriate) will be estimated for each treatment arm.

No formal interim analysis will be conducted for this study. As this is an open-label study, the sponsor may conduct reviews of the data, including MRI data, during the course of the study for the purpose of safety assessment or to support regulatory submissions. Interim safety and efficacy data after approximately 50% of the total sample size has been randomized in the study will be prepared and summarized to support presentation of initial results to India BoH.

1.3. Schedule of Activities

The SoA table provides an overview of the protocol visits and procedures. Refer to the STUDY ASSESSMENTS AND PROCEDURES section of the protocol for detailed information on each procedure and assessment required for compliance with the protocol.

The investigator may schedule visits (unplanned visits) in addition to those listed in the SoA table, in order to conduct evaluations or assessments required to protect the well-being of the participant.

Visit Identifier	Day -28 Screening	Day 1 Baseline	Day 15±1 Week 2	Day 29±2 Week 4	Day 57±3 Week 8	Day 85±3 Week 12 EOT	EOS, 4 weeks post EOT±3 days
	Visit 1	Visit 2	Visit 3	Visit 4	Visit 5	Visit 6	Follow-up
Informed Consent and Assent, as applicable	х						
Demographics, Medical History	Х						
Inclusion/Exclusion Criteria	Х	Х					
Physical Examination ^a	Х	Х				Х	
Vital Signs	Х	Х	Х	Х	Х	Х	Х
Height	Х						
Weight	Х	Х					
Chest X-ray	Х						
ECG	Х					Х	
Clinical Chemistry, Hematology (including coagulation panel), Lipid Profile ^b	Х			Х		Х	
HIV, HBsAg, HCV	Х						
TB test (as per site standards)	Х						
Knee MRI for adolescent participants 12 to <18 years of age ^c	Х						

Visit Identifier	Day -28 Screening	Day 1 Baseline	Day 15±1 Week 2	Day 29±2 Week 4	Day 57±3 Week 8	Day 85±3 Week 12 EOT	EOS, 4 weeks post EOT±3 days
	Visit 1	Visit 2	Visit 3	Visit 4	Visit 5	Visit 6	Follow-up
Serum Pregnancy test (for WOCBP) or FSH	х						
Urine Pregnancy test (for WOCBP only)		Х	Х	Х	X	Х	Х
IGA	Х	Х	Х	Х	Х	Х	
EASI	Х	Х	Х	Х	Х	Х	
SCORAD	Х	Х	Х	X	X	Х	
Photography for AD lesion ^d		Х				Х	X
POEM		Х	Х	X	X	Х	
ADCT		Х	Х	X	X	Х	
PP-NRS ^e	Х						
Randomization		Х					
Dispense Investigational Product		Х	Х	Х	X		
Investigational Product Administration		Х	Х	X	X	Х	
Investigational Product Accountability			Х	X	X	Х	
Contraception check ^f	Х	Х	Х	Х	X	Х	Х
C-SSRS	Х	Х	Х	X	Х	Х	Х
AEs, SAEs and Concomitant Medication Monitoring	X			·	·		X

Visit Identifier	Day -28 Screening	Day 1 Baseline	Day 15±1 Week 2	Day 29±2 Week 4	Day 57±3 Week 8	Day 85±3 Week 12	EOS, 4 weeks post EOT±3
	U U					EOT	days
	Visit 1	Visit 2	Visit 3	Visit 4	Visit 5	Visit 6	Follow-up

a. Complete physical examinations will be conducted at Screening and EOT. Brief physical examinations will be conducted at Baseline. Refer to Section 8.2.1 for details of physical examinations.

b. Clinical chemistry includes: urea, sCr, sCysC (at Screening only), estimated creatinine clearance, AST, ALT, TBili, alkaline phosphatase. The lipid profile will include total cholesterol, LDL, VLDL, HDL, and triglycerides. Hematology includes: hemoglobin, WBC, neutrophils (%, absolute), lymphocytes (%, absolute), platelets, and coagulation panel (APTT, PT/INR). Laboratory tests with abnormal results may be repeated once during the screening period; the last value will be used to determine eligibility. Fasting lipid profile panel require at least an 8 hour fast. If possible, participants should comply with fasting requirements at those visits detailed above.

c. This only applies for participants who were <18 years of age at the screening visit. Further substudy details like post baseline MRI conduct and other activities will be mentioned in Section 10.10 (Appendix 10).

d. Refer to Section 8.1.6 for details of photography.

e. PP-NRS evaluation will be conducted at Screening to evaluate AD severity.

f. Review and record contraceptive method and results of pregnancy testing. Confirm that the participant is adhering to the contraception method(s) required in the protocol. Refer to Appendix 4 for contraceptive guidance.

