4. STUDY DESIGN

4.1. Overall Design

This is a randomized, open-label, parallel-group study to assess the safety and efficacy of orally administered tablets of abrocitinib 100 mg and 200 mg QD in participants aged 12 years and older with moderate to severe AD in India. A total of approximately 200 participants will be enrolled from approximately 10 sites in India. Approximately 200 participants will be randomly assigned to study intervention. Safety endpoints will be assessed throughout the entire study. Secondary efficacy assessments are conducted from Screening to EOT visit.

After providing informed consent or, for minor age participants, informed consent of the legally authorized representative (parent/guardian) and assent of the study participant, participants will be assessed for study eligibility at the Screening visit. Participants will undergo screening within 28 days prior to randomization. Use of screening procedures exceeding 28 days prior to randomization should be discussed with the Pfizer medical monitor.

During the screening period, systemic treatments for AD will be washed out, as applicable, according to eligibility requirements (refer to Inclusion and Exclusion Criteria in Section 5.1 and Section 5.2, respectively). Eligible participants must have a documented history, within 6 months of the screening visit, of inadequate response or intolerance to treatment with medicated topical therapy for at least 4 weeks or must have required systemic therapies for control of their disease.

Eligible participants must meet the eligibility criteria at baseline. Participants who meet eligibility criteria at baseline will undergo Day 1 assessments and be randomized in a 1:1 ratio to receive abrocitinib 200 mg QD or abrocitinib 100 mg QD in an open-label fashion.

The total treatment period is 12 weeks. All participants will undergo a 4week offtreatment safety follow-up period thereafter.

This study protocol also includes a substudy evaluating whether abrocitinib has any potential effects on adolescent bone with regard to bone safety findings in knee MRI. All adolescent

participants 12 to <18 years of age will continue to receive study intervention until 1 year after randomization in the main study. Section 10.10 (Appendix 10) contains complete information regarding the substudy.

For study estimands, refer to Section 3.

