 - In the opinion of the investigator or Pfizer (or designee) exclusion is required.

Prior/Concomitant Therapy:

- 8. Prior treatment with systemic JAK inhibitors.
- 9. Participants who are vaccinated with live attenuated vaccine within the 6 weeks prior to the first dose of abrocitinib or who are expected to be vaccinated with these vaccines during treatment or during the 6 weeks following discontinuation of abrocitinib.

10. Have received any of the following treatment regimens specified in the timeframes outlined below:

Within 1 year of first dose of study intervention:

• Prior treatment with non B cell-specific lymphocyte depleting agents/therapies (eg, alkylating agents [eg, cyclophosphamide or chlorambucil], total lymphoid irradiation, etc.). Participants who have received rituximab or other selective B lymphocyte depleting agents (including experimental agents) are eligible if they have not received such therapy for at least 1 year prior to study baseline and have normal CD 19/20+ counts by FACS analysis.

Within 12 weeks of first dose of study intervention:

• Biologic drugs that have immunomodulatory properties or could be used to treat AD: within 12 weeks of first dose of investigational product or 5 half-lives (if known), whichever is longer.

Other biologics without immunomodulatory properties (eg, insulin) are permissible at the judgement of the Investigator.

Within 4 weeks of first dose of study intervention:

 Use of oral immunosuppressive drugs (eg, CsA, azathioprine, methotrexate, systemic corticosteroids, mycophenolate-mofetil, IFN-γ) within 4 weeks of first dose of study intervention or within 5 half-lives (if known), whichever is longer.

NOTE: Systemic corticosteroids must be discontinued before Study Day 1, but a specific timeframe for discontinuation prior to first dose of abrocitinib is not required.

NOTE: Corticosteroid inhalers and intranasal sprays are permissible.

NOTE: Ophthalmic corticosteroids are permissible.

Within 1 week of first dose of study intervention:

• Anti-platelet drugs.

Note: low dose acetyl salicylic acid (<100 mg QD) is permitted, for the purpose of cardiovascular prophylaxis, at the discretion of the investigator.

11. Require treatment with prohibited concomitant medication(s) or have received a prohibited concomitant medication.

Prior/Concurrent Clinical Study Experience:

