8.2. Safety Assessments

Planned time points for all safety assessments are provided in the Schedule of Activities. Unscheduled clinical laboratory measurements may be obtained at any time during the study to assess any perceived safety issues.

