c. Participants who turn 18 years during the main study will only have baseline MRI. Participants who have completed 3 months of treatment in the main study and turn 18 years of age during the substudy will be required to attend an early termination visit with an MRI scan.

d. AEs and SAEs are recorded/reported as per Section 8.3.

e. Visits corresponding to main visits. Week 12 visit is End of treatment visit for main study. For substudy participants, activities will be performed as per the substudy schedule of activities.

f. Clinical chemistry includes: urea, sCr, sCysC (at Screening only), estimated creatinine clearance, AST, ALT, TBili, alkaline phosphatase. The lipid profile will include total cholesterol, LDL, VLDL, HDL, and triglycerides. Hematology includes: hemoglobin, WBC, neutrophils (%, absolute), lymphocytes (%, absolute), platelets, and coagulation panel (APTT, PT/INR). Laboratory tests with abnormal results may be repeated once during the screening period; the last value will be used to determine eligibility. Fasting lipid profile panel require at least an 8 hour fast. If possible, participants should comply with fasting requirements at those visits detailed above. For all adolescent participants for the substudy, laboratory tests will be performed at Screening, Week 4 and Week 12 as per the main study SoA, as well as at the ET/EOT visit of the substudy.

g. Review and record contraceptive method and results of pregnancy testing. Confirm that the participant is adhering to the contraception method(s) required in the protocol. Refer to Appendix 4 for contraceptive guidance.

Primary substudy objective(s):		Primary substudy endpoint (as secondary endpoints for B7451094):	
•	To evaluate the potential effects of abrocitinib on bone development in adolescent participants 12 to <18 years of age, as assessed by knee MRI.	•	The proportion of bone safety findings in knee MRI 1 year after randomization in adolescent participants exposed to abrocitinib 100 mg and 200 mg QD.

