## 3.4. Baseline Variables

For all safety and efficacy analyses, baseline value is defined as the result of the last assessment performed prior to first dose of study treatment.

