# 6.6.2. Laboratory Data

Laboratory data will be listed and summarized according to CaPS. Laboratory parameters will be summarized descriptively at baseline, Week 4 and EOT visits, and will include the observed and change from baseline values.

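### Laboratory change from baseline starts from a Screening sample that can fall before or during washout of systemic AD drugs, so for those participants it mixes drug withdrawal with the abrocitinib effect

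*Protocol*

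**What the plan says.** Protocol 1.3 schedules the panel, "Clinical Chemistry, Hematology (including coagulation panel), Lipid Profile", at Screening, Week 4 and Week 12. Footnote f of the substudy schedule (Protocol 10.10.2) reads the main schedule the same way: "laboratory tests will be performed at Screening, Week 4 and Week 12 as per the main study SoA". Day 1 is labelled Baseline and repeats vital signs, weight, IGA, EASI and SCORAD, but no blood panel.

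Two routes to another pre-dose result exist. Footnote b to the main schedule says "Laboratory tests with abnormal results may be repeated once during the screening period; the last value will be used to determine eligibility". Protocol 8.2 adds "Unscheduled clinical laboratory measurements may be obtained at any time during the study to assess any perceived safety issues". Neither is a planned baseline.

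SAP 3.4 applies one rule to all safety and efficacy analyses: "baseline value is defined as the result of the last assessment performed prior to first dose of study treatment". SAP 6.6.2 then states "Laboratory parameters will be summarized descriptively at baseline, Week 4 and EOT visits, and will include the observed and change from baseline values".

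On washout, Protocol 4.1 says "During the screening period, systemic treatments for AD will be washed out, as applicable, according to eligibility requirements". Exclusion criterion 10 (Protocol 5.2) has a 4-week or 5-half-life entry, whichever is longer, that begins "Use of oral immunosuppressive drugs (eg, CsA, azathioprine, methotrexate, systemic corticosteroids, mycophenolate-mofetil". A NOTE under that entry says systemic corticosteroids must be stopped before Day 1 but sets no particular interval. Inclusion criterion 2 (Protocol 5.1) admits, as one of several routes, people whose disease has needed systemic therapy.

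**The concern.** A change score is read as the effect of starting the study drug. That reading needs the baseline to be measured in the state the participant was in when dosing began. Efficacy scores meet this because they are repeated on Day 1. The laboratory panel does not, because its only scheduled pre-dose draw sits at the start of the period in which earlier systemic treatment may be withdrawn.

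Decreased lymphocytes, decreased platelets and altered lipids are listed risks in Protocol 2.3.1. The Phase 2b summary in Protocol 2.2.2 reports dose-dependent platelet decreases that levelled off at Week 4, which is a scheduled comparison point here. There is no placebo arm, and SAP 5.1 plans estimation separately in each arm. A shift caused by withdrawal would therefore sit inside the reported change with nothing in the tables to show it. The subset analysis in SAP 6.4 does not help: it covers efficacy endpoints only and splits by AD therapy permitted during the study.

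**Working it through.** **The plan's own figure.** Protocol 9.5 gives a maximum margin of error of 10% with 100 per arm. The 95% half-width at a proportion of 0.5 is 1.96 × √(0.25/100) = 9.8%, which agrees. The point does not touch this figure; only n = 100 is used below, for scale.

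**Where the sample falls in washout.** Let the baseline sample be s days before first dose. Under the 4-week rule the earlier drug was stopped at least 28 days before first dose, so at sampling the participant has been off it for at least 28 − s days:

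| s (days before first dose) | Minimum days off a 4-week drug |
|---|---|
| 28 | 0 |
| 21 | 7 |
| 14 | 14 |
| 7 | 21 |

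Inside the 28-day window the sample is at the start of washout or part-way through it. It can be on drug in two cases: screening longer than 28 days (28 − s turns negative), or systemic corticosteroids, for which the NOTE sets no minimum interval.

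**Time spanned by the change score.** Week 4 is Day 29 and Week 12 is Day 85, so they fall 28 and 84 days after Day 1. From a sample at s = 28 the spans are 28 + 28 = 56 and 84 + 28 = 112 days.

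**Size, under assumption.** Let D be the true mean abrocitinib change, f the share whose baseline sample precedes the end of washout, and w the mean shift from stopping the earlier drug in those participants. The expected reported mean change is D + f × w. Let r be the size of w relative to D, positive when the two oppose. Then reported/true = 1 − f × r. The documents give neither f nor w, so both are assumed:

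| f | r = 0.5 | r = 1 | r = 2 | r = −1 (same direction) |
|---|---|---|---|---|
| 10% | 0.95 | 0.90 | 0.80 | 1.10 |
| 30% | 0.85 | 0.70 | 0.40 | 1.30 |
| 50% | 0.75 | 0.50 | 0.00 | 1.50 |

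**Against sampling error.** The 95% half-width of a mean change at n = 100 is 1.96/√100 = 0.196 SD. For the bias f × w to exceed it, w must exceed 0.196/f: 1.96 SD at f = 10%, 0.65 SD at 30% and 0.39 SD at 50%. With few participants in washout the bias is likely to be lost in the noise; with many it need not be.

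**The case against.** A reader might infer that this baseline hides the listed risks and makes the safety tables look too favourable. The documents do not support that. They do not say how stopping any of these drugs moves platelets, lymphocytes or lipids, and the same formula exaggerates a change when the shift runs the same way as abrocitinib. They do not say how many participants need washout either: Protocol 4.1 qualifies it by applicability, and the systemic route in criterion 2 is about treatment history, not current use.

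A reader might also infer that every affected participant has an on-drug baseline and off-drug later values. Neither half is assured. A 4-week drug has at the latest just been stopped when the sample is drawn inside the window. Protocol 6.8.3 allows systemic corticosteroid rescue after Week 4, so some Week 12 values may themselves be on corticosteroid.

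Other safeguards are real. SAP 6.6.2 lists laboratory data and summarizes observed values at Week 4 and EOT. Protocol 8.2.5 sends clinically relevant laboratory changes to the AE section of the CRF. Primary AE incidence is not calculated from the laboratory baseline. Randomization balances any washout effect between the two doses on average. When screening overruns, Protocol 8 waives rescreening only if pre-dose laboratory results meet eligibility, which may produce a newer sample.

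All of this limits the point without removing it. Observed post-dose values supply no clean pre-treatment reference. The dose contrast cannot recover the change within an arm, and SAP 5.1 plans no such contrast. Repeating only abnormal results makes the baseline selective and does not align it with the end of washout.

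**Conclusion.** The point holds for a subgroup of unknown size. For participants who stop a systemic AD drug during screening, the planned laboratory change from baseline combines withdrawal with the abrocitinib effect and could hide or exaggerate a change. The timing follows directly from the schedule, SAP 3.4 and the washout text. The size does not: the range of 0.00 to 1.50 times the true change is the span of the assumed f and r, not an estimate for this trial.

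The consequence is confined to the interpretation of descriptive change tables. No sample-size figure, hypothesis test or primary result is affected. It is worth correcting because the quantities concerned are named risks and the correction is cheap.

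Separately, criterion 10 names systemic corticosteroids in the 4-week entry while its NOTE sets no interval. The sponsor must reconcile the two, since they determine how long a participant has been off drug at the baseline sample.

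**What to change.** In SAP 6.6.2, add laboratory change from baseline either excluding, or split by, participants who took a systemic AD drug within 4 weeks or 5 half-lives (whichever is longer) before the sample that serves as their baseline. A split is more informative because it shows both groups. Where a repeat or unscheduled result is the last before dosing, count the window back from that date.

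Protocol 6.8 already requires start and end dates for medication in use at enrollment or taken during the study, screening included. It does not expressly cover a drug stopped shortly before consent, so the SAP should name the source for those dates; criterion 10 cannot be checked without them.

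The cost is one extra table with a smaller n. If 10%, 30% or 50% were excluded, 90, 70 or 50 per arm would remain, and the half-width of a mean change would go from 0.196 SD to 1.96/√90 = 0.21, 1.96/√70 = 0.23 or 1.96/√50 = 0.28 SD. The restricted table describes only participants without recent systemic treatment, so it should accompany the full table, not replace it.

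Optional, if enrolment allows: draw the existing panel pre-dose on Day 1 and use it as the laboratory baseline, keeping the Screening sample for the exclusion limits. The spans to Week 4 and Week 12 would then be 28 and 84 days. This needs a protocol amendment and one more draw on top of the estimated 50 mL. It helps only partly for systemic corticosteroids, which under the NOTE may be stopped just before Day 1. Moving the Screening draw to the end of washout is not a practical substitute: for a 4-week drug stopped on Day −28, washout ends at Day 1, after eligibility has to be confirmed.
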